# 7.1 Safety Follow-up Evaluations

A safety follow-up visit will occur when subjects permanently stop study treatment for whatever reason (toxicity, progression, or at discretion of site investigator) and will be performed 30 days ( $\pm$ 7 days) after the last dose of treatment. Subjects who have an ongoing  $\geq$  grade 2 or serious AE (SAE) at this visit will continue to be followed until the AE resolves to  $\leq$  Grade 1 or baseline, is deemed clinically insignificant, and/or until a new anti-cancer treatment starts, whichever is earlier.

#### 7.2 Long Term Follow-up Evaluations

All subjects will be followed until documented disease progression. Subjects who discontinue treatment for any reason without documented disease progression will be followed for disease progression every 2 months ( $\pm 14$  days) for 6 months.

Once disease progression is documented, subjects will enter a survival follow up period every 2 months ( $\pm 14$  days) for 6 months from the time of documented progression.

Follow up may be accomplished via clinic visit, phone call, or other avenues as appropriate.

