2: See section 5 for treatment plan.

3: A window of  $\pm 3$  days will be applied to all cycle 1 and 2 treatment visits; a  $\pm 7$ -day window will apply for maintenance visits.

4: Subjects without documented disease progression will be followed for disease progression every 2 months ( $\pm 14$  days) for 6 months. Once disease progression is documented, subjects will enter a survival follow up period: every 2 months for 6 months from the time of documented progression.

5: Medical history will capture genetic sequencing results/cytogenetics report, prior substance abuse, organ transplant, history of liver disease and family history of cancer.

6: Drug diary review will be performed on Day 1, prior to dispensing the next cycle of venetoclax.

7: For women of childbearing potential (WOCBP): urine or serum  $\beta$ hCG, within 7 days prior to study registration. If a urine test is positive or cannot be confirmed as negative, a serum pregnancy test will be required.

8: CBC should be performed daily while subjects are in the hospital. Basic metabolic panel (calcium, carbon dioxide, chloride, creatinine, glucose, potassium, sodium, urea nitrogen), coags and uric acid measurements will be performed at least every 8 hours during the ramp up and every 8-12 hours during Cycle 1 Days 1-3 to monitor for tumor lysis syndrome. Subsequently, recommend basic metabolic panel and liver function tests be performed at least three times weekly during the induction phase. Uric acid should be evaluated at further intervals at the discretion of the investigator. Recommend measuring coags weekly during the remainder of the induction phase. During consolidation, recommend measuring these labs daily while patient is in hospital and at least weekly when outpatient, at the discretion of the treating physician. During maintenance, recommend measuring these labs at least once every two weeks when outpatient, at the discretion of the treating physician.

9: Bone Marrow Aspirate and Biopsy and/or evaluation of extramedullary site with immunophenotyping, cytochemistry, and cytogenetics (karyotype  $\pm$  FISH): to be completed at pre-treatment (within 14 days), Day 28  $\pm$  3 days during cycles 1 and 2, and  $\pm$  14 days pre-treatment cycle 7 day 1 (i.e. ~6 mo), pre-treatment cycle 13 day 1 (i.e. ~12 mo), and relapse. Patients in PR at the end of consolidation should have a repeat BM assessment after one month of maintenance.

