#### 9.2 Definitions of Survival Endpoints for AML

Overall Survival	All evaluable patients entered into trial; measured from the date of entry to the date of death from any cause; patients not known to have died at last follow- up are censored on the date they were last known to be alive				
Relapse-free Survival	Only patients achieving CR or CRi; measured from the date of achievement of a remission until the date of relapse or death from any cause; patients not known to have relapsed or died at last follow-up are censored on the date they were last examined				
Event-free Survival	All patients entered into trial; measured from the date of entry to the date of treatment failure, disease relapse, or death from any cause; patients not known to have any of these events are censored on the date they were last examined				
Adapted from European LeukemiaNet. 					

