# 12.6.2 Analysis Plans for Secondary Objectives

Descriptive characteristics of all adverse effects of GO in combination with Venetoclax (using CTCAE v5 criteria) will be reported; and the efficacy of the combination in achieving ORR (includes CR/CRi) and anti-leukemic activity (includes CR/CRi/PR), as defined by the revised IWG criteria), RFS, EFS, and OS in subjects. The effects of therapy on quality of life, fatigue, and physical function at D0 (trial entry) and the end of every other month for 1 year (see section 8.1) will be reported and analyzed using generalized linear modeling.

All time-to-event outcomes (e.g. survival) will be calculated using Kaplan Meier methods and exploratory log-rank tests will be used to compare treatment effect between groups based on genomic MRD, CD33 DNA polymorphisms, BH3 profiling and anti-apoptosis protein levels in PB MBCs at presentation and after 1 week of Venetoclax.

*Sample size permitting:* Hazard ratios (HR) and 95% CIs will be produced. Time-to-event outcomes with a competing or semi-competing risk (e.g. CIR) will be analyzed using cumulative incidence curves and exploratory comparisons between arms will be made using Grey's test. Rate ratios and 95% CIs will be presented. Chi squared tests will be used to assess the treatment effect between cohorts for all categorical variables and t-tests or Mann Whitney tests will be applied for continuous measures as appropriate.

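### OS follow-up stops 6 months after progression, or 6 months after leaving treatment without it, so Kaplan-Meier OS after about month 7 is open to informative censoring

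*Combined protocol and SAP*

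**What the plan says.** Section 7.2 contains three follow-up rules.

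- General rule: "All subjects will be followed until documented disease progression".
- Off treatment without progression: "Subjects who discontinue treatment for any reason without documented disease progression will be followed for disease progression every 2 months", for 6 months. The text does not say whether survival is tracked after that.
- After progression: survival contact every 2 months, "for 6 months from the time of documented progression".

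Footnote 4 of the study calendar repeats the last two rules, the third as "every 2 months for 6 months from the time of documented progression".

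Section 9.2 defines OS as "measured from the date of entry to the date of death from any cause", and patients not known to have died "are censored on the date they were last known to be alive". Section 12.6.2 adds: "All time-to-event outcomes (e.g. survival) will be calculated using Kaplan Meier methods". I found no later vital-status collection and no method for censoring that depends on disease course. Section 5.6 lets patients leave for transplant at any point, so exits without progression are expected.

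**The concern.** Kaplan-Meier assumes that a patient censored at a given time has the same future risk of death as those still followed. Here the censoring time is set by events that predict death. A patient who progresses leaves the OS risk set 6 months later if alive, while patients still on treatment without progression stay in it. Patients who stop treatment without progression may also leave after 6 months, and some of them, such as those going to transplant, may have a good outlook.

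OS is a secondary objective (section 2.1.2). Section 8.1.1 correlates MRD kinetics with OS, and section 12.6.2 plans exploratory log-rank tests between biomarker groups. Groups that progress at different speeds would be censored at different speeds. A reported confidence interval does not cover this kind of error.

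**Working it through.** **Inputs from the documents.** First scheduled marrow at day 28 (section 5.4). Survival follow-up of 6 months after progression (7.2). Enrolment 18 months, study 30 months and N = 15-24 (synopsis). Potential follow-up is therefore 30 - 18 = 12 months for the last patient and 30 for the first. The plan states no OS rate, event count or precision, so there is no OS figure to reproduce. All prognostic inputs below are assumptions.

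**Onset.** The earliest progression-driven censoring at a scheduled assessment is about month 1 + 6 = month 7. Bias at 6 months is zero.

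**Hand example A: progression rule only.** Half the patients have progression documented at month 1 and then median survival of 4 months. The other half stay in follow-up with median survival of 12 months. All times are exponential.

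- OS at month 7: 0.5 × 2^(-6/4) + 0.5 × 2^(-7/12) = 0.177 + 0.334 = 0.510. The estimate is correct up to here.
- At month 7 the surviving progressors (0.177) are all censored. From then on Kaplan-Meier sees only the other half.
- Kaplan-Meier at month 12: 0.510 × 2^(-5/12) = 0.510 × 0.749 = 0.382.
- True OS at month 12: 0.5 × 2^(-11/4) + 0.5 × 2^(-12/12) = 0.074 + 0.250 = 0.324.
- Bias: 0.382 - 0.324 = +5.8 points.

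**Hand example B: both 6-month limits.** As A, but half of the second group (25% of all patients) leave without progression at month 3, with no deaths before that and median survival of 36 months afterwards. They are last contacted at month 9.

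- Kaplan-Meier at month 7: 0.177 + 0.25 × 2^(-4/36) + 0.25 × 2^(-7/12) = 0.177 + 0.231 + 0.167 = 0.575.
- Months 7 to 9: factor (0.223 + 0.149)/(0.231 + 0.167) = 0.932, giving 0.536 at month 9.
- Month 12: Kaplan-Meier 0.536 × 2^(-3/12) = 0.451; true 0.074 + 0.210 + 0.125 = 0.410. Bias +4.1 points.
- Month 24: Kaplan-Meier 0.536 × 2^(-15/12) = 0.225; true 0.009 + 0.167 + 0.063 = 0.239. Bias -1.3 points.

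The sign depends on who is lost.

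**Simulation with staggered entry.** Assumed: 30-45% responders; median time to progression 6-10 months in responders and 1-2 in others; median post-progression survival 3-8 months; 2% per month death without progression; 18-month accrual; closure at month 30. Bias is in percentage points.

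| Setting | 6 mo | 12 mo | 18 mo |
|---|---|---|---|
| No exits without progression | 0 | +3.0 to +6.6 | +4.6 to +11.2 |
| Responders also exit for transplant (median 4 months to exit, 36 months' survival after) | 0 | -1.4 to +4.9 | -4.9 to +9.1 |

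**Wider grid.** There were 540 scenarios: 30-70% refractory, post-progression median 2-6 months, 0-60% of the rest marked for transplant, and variable post-progression survival. The bias was -0.3 to +5.2 points at 9 months, -1.6 to +8.9 at 12 (above +0.5 point in 77% of scenarios) and -9.1 to +12.3 at 18. If patients off treatment without progression were followed without the 6-month limit, the median bias was upward throughout (+1.6 to +5.3 points across 9-24 months). So the two sentences of 7.2 affect the answer. When death hazards before and after progression were set equal, the bias was zero.

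**Information lost.** With 50% refractory, median time to progression of 5 months in the rest and post-progression median of 4 months, the mean number at risk at month 12 falls from 6.8 to 3.8 for N = 24, and from 4.3 to 2.4 for N = 15.

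**Sampling error.** Half-width = 1.96 × √(p(1-p)/N). For p = 0.26, N = 24: 1.96 × 0.0895 = 18 points. For p = 0.40, N = 15: 1.96 × 0.1265 = 25 points.

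**The case against.** **Direction.** A reader might infer that the OS curve is simply inflated. The documents do not support that. It would require that patients censored 6 months after progression always die faster than those still followed. The second limit can remove patients who are doing well, and long survivors after progression act the same way. This objection stands, and it is why the direction at 18 months and later is left open.

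**Benchmark.** A reader might also set the curve against the 11-month median survival in section 1.2.1. That figure is for fractionated GO without venetoclax and is cited to explain the GO schedule. The plan sets no OS threshold, comparator or decision rule. If post-progression survival is short, the median barely moves anyway: with a 3-month post-progression median and no other exits, median OS shifts by at most 0.1 month. With 8 months the shift is 0.8-2.4 months.

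**Consequence.** This is a phase Ib trial with a DLT endpoint, OS is only estimated, and the half-width of 18-25 points is several times the bias. That lowers the priority. It does not justify leaving obtainable death dates uncollected, since the follow-up rule both adds bias and shrinks the risk set.

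**Contradiction.** The first two sentences of 7.2 can be read as a general rule followed by a specific one for patients off treatment. That is a fair reading, so the text needs clarifying. It still leaves survival follow-up undefined for patients who have not progressed when their 6 months end.

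**Conclusion.** The concern holds in limited form. As written, the plan ties OS censoring to progression and to the way treatment ends, and Kaplan-Meier does not allow for this. OS to 6 months is sound. After about month 7 it is open to bias, probably upward at 9-12 months: about +3 to +7 points at 12 months if few patients leave without progression, and about -1 to +5 if many responders leave for transplant. No direction can be claimed at 18 months or later.

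These sizes rest on assumed response, progression and survival times, because the documents give none for this combination. The existence of the problem rests only on the wording of 7.2, 9.2 and 12.6.2, together with progression being a predictor of death. The DLT/MTD result is untouched. This is a worthwhile inexpensive improvement and does not threaten the trial.

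**What to change.** Amend section 7.2 and calendar footnote 4 so that vital status is collected every 2 months, by phone or record review, for every treated patient until death or study close (30 months), regardless of progression or reason for stopping treatment. In the same amendment, reconcile the first two sentences of 7.2 so that disease follow-up and survival follow-up are stated separately for patients who stop treatment without progression.

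With such follow-up, simulated Kaplan-Meier OS matched true OS within 0.1 point in the main scenarios, so the fix works whichever way the bias would have gone.

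The cost is a short amendment and some extra phone or record checks for at most 24 patients, within the planned study duration. Section 7.2 already allows phone contact.

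If this is not adopted, report Kaplan-Meier OS only to 6 months, which needs no new data.

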#### 8. **BIOSPECIMEN STUDIES AND PROCEDURES**

#### 8.1 Correlative Studies

- 8.1.1 Longitudinal assessment of genomic minimal residual disease (MRD) with droplet digital PCR (ddPCR) will determine the kinetics and depth of response and its association with RFS and OS. ddPCR is a novel technology capable of detecting gene mutations in as few as 1 in 50,000 cells, providing a highly sensitive platform for AML MRD measurement. DNA extracted from pretreatment patient bone marrow or peripheral blood mononuclear cells (PBMC) will undergo targeted deep sequencing of recurrently mutated genes in AML and/or whole exome sequencing to identify somatically-acquired leukemia-associated gene mutations. These mutations will be confirmed to be somatic by Sanger resequencing of both tumor and germline (derived from buccal swab) DNA. ddPCR will then detect these mutations in serial post-treatment samples (4 time points: end of induction, end of consolidation, and at 6 months and 12 months) using genomic DNA from bone marrow and/or PBMC as well as plasma-based cell-free DNA to determine the presence of genomic MRD at each time point. Both the rate and maximal level of reduction of leukemia-associated gene mutations will be correlated with RFS and OS. The measurement of multiple genes per patient will allow assessment of clonal dynamics in the MRD state and the relative clearance of leukemic versus pre-leukemic cells (defined as clones containing all gene mutations identified pre-treatment or those containing only a subset of those gene mutations, respectively). These experiments will be performed at the laboratory of [name].
- **8.1.2** Association of CD33 cell-surface expression and *CD33* single nucleotide polymorphisms (SNP) and somatic mutations with response to the combination of GO and Venetoclax will be determined based on serial genomic MRD levels, CR, and RFS. The presence of splice acceptor SNPs that lead to alterative splicing of *CD33* that eliminates the IgV portion of the molecule to

which GO binds has recently been shown to adversely influence clinical effectiveness of GO in trials including GO alone or in combination with chemotherapy. In order to study the impact of such *CD33* variants in this trial, all coding exons and adjacent intronic sequences of *CD33* will be sequenced from genomic DNA extracted from pre-treatment samples and paired buccal swabs to identify germline SNPs and acquired somatic mutations. Similar sequencing will be performed on any relapsed specimens as well to determine emergence of secondarily-acquired *CD33* mutations. The presence of isoform altering mutations will be confirmed with isoform specific qPCR of mRNA extracted from pre-treatment samples. Finally, cell surface expression of CD33 isoforms including or lacking the IgV region will be determined using flow cytometry with isoform specific antibodies (anti-CD33 clones P67.6 and HIM3-4, respectively). These experiments will be performed at the laboratory of [name].

- **8.1.3** Identification of clonal evolution and secondarily acquired mutations in refractory and relapsed patient samples may reveal mechanisms underlying treatment failure. For patients who do not respond to the induction and consolidation cycles of the investigational therapy or who relapse after initial response, whole exome sequencing may be performed on germline controls (derived from buccal swabs), pre-treatment tumor samples, and tumor samples obtained at the time of treatment failure in order to identify the presence of primary or secondary acquisition of mutations that may be related to the mechanisms of treatment failure. For relapsed patients, ddPCR will be used to track mutations acquired or enriched in the relapse clone into the pre-treatment and CR samples in order to determine if the relapsed clone acquired the mutations after treatment or if a minor preexisting clone was enriched as a result of treatment. These experiments will be performed at the laboratory of [name].
- **8.1.4** BCL-2 Family Protein Analysis prior to, and after Venetoclax exposure may reveal adaptive changes in anti-apoptotic protein expression. Leukocytes isolated from pretreatment and Day+3 (C1D3) peripheral blood will be analyzed by semi-quantitative Western blot analysis for BCL-2, BCL-XL and MCL-1 expression. If sufficient samples are available then PBMNC samples from pretreatment and Day+3 will also be permeabilized, incubated with fluorescent antibodies to BCL-2, BCL-XL and MCL-1, and expression measured by flow cytometry. Analysis will also be performed on relapse samples (if this occurs). These experiments will be performed at the University of Illinois in the laboratory of [name].

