# 2.1.3 Exploratory Objectives

- Longitudinal assessment of genomic minimal residual disease (MRD) to determine the kinetics of response and the association with relapse-free survival.
- Explore the impact of CD33 variants, and the degree of CD33 expression on leukemic blasts, on the response rates and relapse-free survival.
- Explore the relationship between leukemic blast BH3 profiling and response rates.

• Explore the relationship between leukemic blast expression of anti-apoptosis proteins (BCL-2, BCL-XL and MCL-1) and response rates.

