# **5.5** Maintenance Phase: (see also section 6.2.2, Tables 7, 8)

Please note that any patient with residual disease (with at least PR) may move onto maintenance regardless of blood counts.

Patients who enter a maintenance phase require platelets  $\geq 50 \ge 10^{9}/L$  and an ANC  $\geq 1.0 \ge 10^{9}/L$ . If a subject presents with a Grade 4 cytopenia for more than 1 week during Maintenance phase, unless it is thought to be due to the underlying disease, venetoclax dosing should be interrupted until platelets  $\geq 50 \ge 10^{9}/L$  and ANC  $\geq 1.0 \ge 10^{9}/L$ .

During Maintenance, for subjects, in CR/CRi, receiving venetoclax who required >1 interruption or delay of study drug administration for grade 4 cytopenias, venetoclax, at dose prescribed for that cohort, should be administered for 21 days out of 28 days during each of the subsequent cycles. If, despite these modifications, a subject continues to have persistent grade 4 cytopenias, venetoclax should be administered for 14 days out of 28 days during each of the subsequent cycles.

If grade 3 cytopenias (i.e., ANC <  $1.0 \times 10^9$ /L and/or platelets <  $50 \times 10^9$ /L) persist please discuss with PI, however those who still continue to have a grade 4 cytopenia should be taken off study.

Venetoclax therapy will be continued daily at the previously assigned dose for as long as patients continue to benefit or until disease progression or unacceptable toxicity.

Patients who enter the maintenance phase in partial remission should have a bone marrow assessment after the first month of maintenance therapy (cycle 3). Those with an improved response should continue with maintenance Venetoclax. Those with stable disease should continue treatment if the drug is well-tolerated and if the primary hematologist believes that Venetoclax is of benefit. If there is disease progression, patients should be taken off study.

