# 8.2.2 Bone marrow aspirate:

Bone marrow aspirate material will be collected will be collected prior to treatment, at the end of the induction cycle (Cycle 1 Day  $28 \pm 3$  days), at the end of the consolidation cycle (Cycle 2 Day  $28 \pm 3$  days), at pre-treatment cycle 7 day 1 (i.e. ~6 months after initial treatment) ( $\pm$  14 days), at pre-treatment cycle 13 day 1 (i.e. ~12 months after initial treatment) ( $\pm$  14 days), and at any time of suspected relapse. Leukocytes from the bone marrow aspirate will be isolated by Ficoll gradient centrifugation and cryopreserved for use in the correlative studies described. See CLM for collection, labeling, processing, and shipping instructions.

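### Using the maximal MRD reduction over samples up to 12 months as a fixed predictor of RFS (from remission) and OS (from entry) builds in guarantee-time bias, usually in favour of deep MRD response

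*Combined protocol and SAP*

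**What the plan says.** The first exploratory objective in section 2.1.3 is "Longitudinal assessment of genomic minimal residual disease (MRD) to determine the kinetics of response and the association with relapse-free survival". Section 8.1.1 sets the post-treatment sampling at "4 time points: end of induction, end of consolidation, and at 6 months and 12 months" and then states: "Both the rate and maximal level of reduction of leukemia-associated gene mutations will be correlated with RFS and OS". It does not define the rate, and it does not say how the maximum is to enter the analysis.

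Section 9.2 restricts RFS to patients in CR or CRi and has it "measured from the date of achievement of a remission until the date of relapse or death from any cause". OS has a different origin: it is "measured from the date of entry to the date of death from any cause".

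Sections 8.2.2 and 8.2.3 tie the two late samples to the start of cycles 7 and 13. For patients who enter maintenance in partial remission, section 5.5 says: "If there is disease progression, patients should be taken off study". Section 6.3 lists documented progression as a reason to end protocol therapy for all patients.

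The analysis text, section 12.6.2, specifies Kaplan-Meier estimates and says that "exploratory log-rank tests will be used to compare treatment effect between groups based on genomic MRD" and other markers. Hazard ratios follow if the sample size permits. No section names a landmark, a time-dependent covariate, a single MRD time point for the survival comparison, or a rule for patients who relapse before a later sample.

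**The concern.** The maximal reduction is known only after the last sample, but the RFS and OS clocks have been running since remission or entry. A patient who relapses at month 4 contributes at most two of the four samples. A patient still in remission at month 12 contributes all four, and so has more chances to record a deep value. If the maximum is treated as though it were known at time zero, long survivors drift into the deep-response group because they survived. This is guarantee-time bias.

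Sections 2.2.3 and 8.2 also allow a sample at relapse, but that sample is unlikely to be the patient's deepest.

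At stake is the reading of a named exploratory objective. The likely error is a hazard ratio that favours deep MRD response when there is no relation, and a larger sample does not remove it.

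**Working it through.** The plan gives no sample size, power or error rate for the MRD analysis, so there is no stated figure to reproduce. The check is whether the described analysis is unbiased when MRD has no relation to outcome.

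**Inputs from the protocol**
- MRD visits at about months 1, 2, 6 and 12 (8.1.1).
- Median RFS of about 6 months after earlier GO treatment, a median survival of 11 months and an ORR of 33% with fractionated GO (1.2.1).
- Median time to relapse of 75 days, about 2.5 months, on venetoclax alone (1.2.2).
- At most 24 patients (Synopsis, 12.3). Remitters: 0.33 × 24 ≈ 8.

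**Assumptions.** Remission at month 1; exponential event times with median 2.5, 6 or 11 months; censoring at 24 months; correlation between a patient's MRD values of 0, 0.5 or 0.8; maximal reduction split at its median; two-sided 5% log-rank test. MRD is seen only while the patient is event-free (RFS) or alive (OS).

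**Step 1: who supplies the late samples.** The share still event-free t months after remission is 2^(−t/median). The four visits fall at t = 0, 1, 5 and 11.

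| Median RFS | Month 1 | Month 2 | Month 6 | Month 12 |
|---|---|---|---|---|
| 2.5 months | 100% | 76% | 25% | 5% |
| 6 months | 100% | 89% | 56% | 28% |
| 11 months | 100% | 94% | 73% | 50% |

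**Step 2: why the number of samples matters.** If a patient's values were independent across visits, the chance that the largest of k values exceeds the single-visit median is 1 − 0.5^k. That is 50% for one sample, 75% for two and 94% for four. Positive correlation narrows these gaps but does not close them.

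**Step 3: simulated null, RFS from remission, median 6 months, no deepening over visits.** There were 4,000 replicates for each of n = 8, 12 and 24.

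| Within-patient correlation | Null HR, deep vs shallow | False positives, n = 8 | n = 12 | n = 24 |
|---|---|---|---|---|
| 0 | 0.63 | 9% | 15% | 20% |
| 0.5 | 0.74 | 7% | 10% | 12% |
| 0.8 | 0.83 | 6% | 9% | 9% |

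At n = 24 the null HR is 0.62, 0.73 and 0.83 for a 2.5-month median, and 0.67, 0.77 and 0.86 for an 11-month median. OS from entry shows the same pattern at n = 24: HR 0.62 to 0.86, false positives 7.5% to 20%. The bias does not shrink with size: at n = 400, median 6 months and correlation 0.8, the null HR is 0.84 and 37% of tests reject.

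**Step 4: the same check with a month-2 landmark.** Only visits up to month 2 are used, and the clock starts there. The median null HR is 0.98 to 1.03 in every setting. Two-sided rejection is 3.5-5.8% at n = 400 and 5-9% at n = 8 to 24. The small-sample excess comes from the asymptotic log-rank test and not from MRD.

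**Step 5: false positives at a realistic size.** A separate null simulation with 8 remitters and no deepening gave two-sided rates of 5-11% for the maximum against 6-8% for the landmark. Rejections favouring deep reduction were 3-10% against 2-4%.

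**Step 6: if reductions deepen over visits.** With an assumed deepening of 0.25 to 1 SD per visit, false positives are 10-41% with 8 remitters (landmark 6-9%). With 12 remitters they are 14-57% or 14-65% in two runs with slightly different medians (landmark 6-8%). The protocol gives no figure for deepening, so this range is purely an assumption.

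**The case against.** The strongest reply is that the biased test is only one reading. Section 8.1.1 says that the maximum will be correlated with outcome, without specifying a split or a log-rank test on it. Section 12.6.2 does not say which MRD measure forms the groups. The endpoint in sections 2.2.3 and 12.2.3 lists MRD by visit. Comparing RFS by MRD status at one visit, among patients still relapse-free then, gives both groups the same guarantee time and is in effect already a landmark analysis. This stands: the log-rank sentence in 12.6.2 does not establish the defect by itself. The exposed text is the maximal reduction in 8.1.1. The rate is exposed only if it is computed over all visits, and it is not if taken from baseline to end of induction.

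A reader might also infer that the planned test will find an association far more often than 5% of the time, always in favour of deep response. The documents do not support that. With about 8 remitters and no deepening, the two-sided excess over a landmark is small. The large figures need an assumed deepening or more remitters than a 33% response rate would give. The direction is usual but not certain: patients may leave for transplant at any point (5.6), or for persistent cytopenia while in remission (5.4). They can then combine few samples with long RFS. The simulations omit this.

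Finally, the analysis is exploratory, with no role in dose selection. That limits the consequence. It excuses imprecision, but not an estimate with a known direction of bias.

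**Conclusion.** The concern holds for the maximal reduction used as a fixed covariate. The text of 8.1.1, taken with the time origins in 9.2 and the cycle-tied samples in 8.2, leads to that analysis, and nothing in 12.6.2 corrects it. The plan does not rule out a landmark; it is silent.

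The main effect is on the estimate: a null HR of about 0.63 to 0.83 at a 6-month median RFS, against about 1.0 with a landmark. The range depends on the assumed within-patient correlation, and the low end needs serial values in one patient to be uncorrelated, which is extreme. The effect on the two-sided error rate is small at about 8 remitters unless reductions deepen over visits. OS is affected as well, though its clock starts at entry and not at remission.

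A reader might infer that every MRD comparison in the plan is invalid, or that the trial's conclusions are at risk. Neither follows. By-visit MRD status among patients still in remission is sound, and the primary endpoint and dose selection are untouched.

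**What to change.** In 8.1.1 and 12.6.2:

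- Define MRD status or reduction, and the rate of reduction, at a fixed early sample.
- Use end of induction as the main landmark and end of consolidation as a second. The order matters because CRi patients without count recovery skip consolidation (5.4) and would be handled poorly by a consolidation landmark alone.
- Start RFS and OS at the landmark, among patients then alive and, for RFS, in remission.
- Report the maximal reduction and the 6- and 12-month values descriptively, or as time-dependent covariates if numbers allow. Do not use them as fixed predictors of RFS from remission or OS from entry. With perhaps 5 to 8 remitters (0.33 × 15 to 0.33 × 24), the descriptive report is the realistic choice.

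The change is to wording only: no new samples, visits or patients. Patients with an event before the landmark leave this exploratory analysis. Those who reach remission only after consolidation enter the RFS comparison at the second landmark. Later deepening of response is not used in the main comparison.
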